1 SYNOPSIS

Title	The Circle Method Observational Project - Circle method for sizing and positioning in bicuspid valves
Background	
The bicuspid aortic valve (BAV) is the most common heart valve abnormality and is associated with a number of cardiac complications, including infective endocarditis, aortic dissection, aortic dilatation, and the development of severe aortic stenosis (AS). Due to its anatomical characteristics BAV has been considered a contraindication to transcatheter aortic valve implantation (TAVI), a standard treatment of AS. However, several recent trials have presented promising results indicating TAVI to be a safe alternative to surgery for low risk patients and more patients with BAV have been considered for TAVI.
 
There are several sizing techniques for TAVI in BAV, including an annular sizing, a supra-annular sizing, and a balloon sizing, yet there is still no consensus on the most appropriate technique. Although annular sizing remains the major approach in most patients with BAV, some BAV anatomies may profit from the supra-annular sizing. Recently published consensus for sizing and positioning the balloon-expandable Edwards SAPIEN 3 transcatheter heart valve (THV) in BAV describes the anatomical features that influence sizing optimization (1). The novel circle technique has also been proposed in the presence of the unique anatomical factors and sizing at the supra-annular level. This method is particularly helpful for visually identifying anatomic features, indicating the sealing zone at the commissures, visually reassuring of the size and position, and treating patients with large annuli. Currently, there are limited data validating the circle method for identifying sizing and positioning for TAVI in BAV patients.

Aim	To validate the circle method for sizing and positioning of SAPIEN 3 THV, using circles to simulate the SAPIEN 3 TAVI at 0, 3, 6, and 9 mm in 3mensio above and below the coronary arteries.
Trial design	Retrospective, non-interventional, 3mensio based analysis in 3 centers (Berlin, Katowice and Cambridge) and at least 60 eligible patients.

Patients	
Inclusion Criteria:
 
 • Patients with bicuspid aortic valves undergoing aortic valve replacement with a balloon expandable valve (SAPIEN 3 / Ultra) • Computed Tomography data available
Primary objectives	
To assess whether patients with bicuspid aortic valves that received a SAPIEN 3 / Ultra THV suffered from fewer complications
 
 • if valve size was identical to the one determined using the circle method 
compared to
 
 • a case where circle method derived valve size is different from the actually implanted valve
Secondary objectives	
To develop recommendations on how to size the valve using the circle method.

Exploratory research questions / endpoints	
We aim to assess whether patients with bicuspid aortic valves that received a SAPIEN 3 / Ultra THV suffered from fewer complications
 
 • if valve size was identical to the one determined using the circle method 
compared to
 
 • a situation where circle method derived valve size is different from the actually implanted valve 
Complications are defined as:
 
 • Death • Stroke • Paravalvular Leakage (PVL) • Pacemaker implantations • Coronary occlusion • Malposition • Fistula to right ventricular outflow tract (RVOT) • Annulus rupture • Sinus sequestration • Valve embolisation
Schedule	
Baseline, Intervention, Discharge, 30 days, 3 months/12 months (according to availability, all retrospective)

Quality assurance / CoreLab	A CoreLab with the 3mensio Software and the most recent update as of January 2021 will be available to assess the CT data matching each patient. The two CoreLab physicians will independently assess the CT data based on the manual provided in the appendix. These data will be collated with the clinical dataset to assess correlations between measurements and complications / outcomes.
Statistics	No pre-specified statistical analyses, explorative approach.
Sample size	Given the limited data for sizing and positioning with the circle method in BAV patients, we aim to include at least 60 patients for this pilot study.

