Annular sizing remains the major treatment approach in most patients with BAV, yet some BAV anatomies may require sizing at the supra-annular level. Because of the unequal-sized leaflets and reduced number of commissures, the orifice in BAV is usually smaller, more asymmetrical, and less circular than in TAV. As a result, the leaflets do not open in the same way during TAVI and conventional

annular sizing may result in over-sizing at the level of the leaflets, leading to more asymmetry and increased risk of trauma related to calcification in the aortic valvular complex (1).

Blackman et al. recently published guidelines for sizing and positioning the balloon-expandable Edwards SAPIEN 3/Ultra transcatheter heart valve (THV) in BAV (1). The consensus describes the following anatomical factors that influence sizing optimization in patients with BAV:

- 1) *Calcification of the raphe*. Severe raphe calcification reduces valve expansion or may cause malpositioning of the transcatheter heart valve (THV), leading to potential undersizing relative to the aortic annulus
- 2) *Calcification of the cusps*. In case of an extreme calcification of the cusps, relative undersizing should be considered as anchoring in the supra-annular space is enhanced.
- 3) *Configuration of the aortic valve*. Relative undersizing may also be considered in patients with a tapered, as opposed to tubular or flared, valve configuration, i.e., where the supra-annular space is smaller.
- 4) *Large annuli*. A large annular area (above the upper limit of the SAPIEN 3 sizing chart) is often the case in patients with BAV and sizing to the supra-annular space should be considered.

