Considering these anatomical variables, the circle technique has been suggested in cases of sizing optimization at the supra-annular level (1). This method includes a projection of an ellipse circle, which is one size smaller than the annulus size, in addition to the circle that is equivalent to the conventional sizing method. The technique is particularly helpful for visually identifying anatomic features, such as excessive calcified raphe, bulky leaflets, or eccentric calcifications in the aortic valvular complex, and preventing major vascular complications. Further advantages of the circle method include the indication of the sealing zone at the commissures, visual reassurance of the size and position, treatment of patients with large annuli, and its easy reproduction. However, as there are no strict thresholds on the sizing of the valve, physicians have to match the circle to the patient's BAV anatomy. The SAPIEN 3 THV has previously shown a good index of circularity, even in BAV (17). Therefore, projecting a circle through the aortic complex is the ideal approach for sizing as well as the positioning of the device. There is, however, limited data validation for the circle approach in patients with BAV.

In view of this, this project aims to validate the circle method for sizing and positioning of the device by evaluating the 30-day and 3-month outcomes of all consecutive patients with BAV undergoing TAVI.

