3.2 PROJECT OBJECTIVES

3.2.1 Primary Objective

The primary objective of this project is to validate the circle method for sizing and positioning of the SAPIEN 3 THV in patients with BAV. In particular we aim to assess whether patients with BAV that received a SAPIEN 3 / Ultra THV suffered from fewer complications if valve size was *identical* to the one determined using the circle method compared to a situation where circle method derived valve size is *different* from the actually implanted valve.

We will use circles to simulate the SAPIEN 3 THV at 0, 3, 6, and 9 mm in 3mensio above and below the coronary arteries.

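### The primary comparison has no conventional-sizing reference, so it cannot by itself show what the circle method adds over annular sizing

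*Combined protocol and SAP*

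**What the plan says.** Section 3.2.1 states: "The primary objective of this project is to validate the circle method for sizing and positioning of the SAPIEN 3 THV in patients with BAV". The same section and the Synopsis turn this into one contrast. Complications are compared "if valve size was identical to the one determined using the circle method" against "a case where circle method derived valve size is different from the actually implanted valve".

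Section 2.1 describes the circle method as projecting a circle "one size smaller than the annulus size, in addition to the circle that is equivalent to the conventional sizing method". It also says: "Annular sizing remains the major treatment approach in most patients with BAV".

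No objective, endpoint or analysis section derives a conventional size for each patient, forms an annular-concordant group, or isolates patients whose circle and annular sizes differ. Section 8.2 analyses the whole study population with unadjusted two-group tests and does not name the groups. The Synopsis states that no statistical analyses are pre-specified. CoreLab readings follow an appendix manual that is not in the text available for this review.

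**The concern.** Because one of the circles is the conventional one, the circle-method size can equal the annular size. A patient in whom they are equal falls into the same group, identical or different, whichever method is being tested. Such a patient can show whether receiving that size went well, but not whether the circle method improved on annular sizing.

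Only patients whose two sizes differ can separate the methods, and the plan never isolates them. On the protocol's own account they may also be the harder cases. Section 2.1 lists severe raphe or cusp calcification, tapered configuration and large annuli as reasons to depart from the annular size, and names calcified raphe and large annulus among the features that may worsen procedural outcome. If operators mostly sized by the annulus, the different group would consist largely of such patients.

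At stake is attribution. A favourable result could be read as validating the circle method, and could feed the sizing recommendations of Section 3.2.2, when it reflects anatomy or adherence to annular sizing.

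**Working it through.** **The plan's own figure.** Section 8.1 gives a mean of 20 patients per site, and Section 4.1 gives three sites: 3 × 20 = 60, which agrees with the stated minimum. The documents give no complication rate, effect size or share of patients with equal sizes. Every risk and split below is therefore an assumption.

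**How patients are classified**

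| Circle and annular sizes | Implanted size | Circle contrast | Annular contrast |
|---|---|---|---|
| Equal | the shared size | identical | identical |
| Equal | another size | different | different |
| Differ | circle size | identical | different |
| Differ | annular size | different | identical |
| Differ | neither | different | different |

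Only rows 3 and 4 separate the methods.

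**No true effect of method.** Assume 60 patients, risk 10% where sizes agree and 30% where they differ whichever size is implanted, discordant patients split equally between the two sizes, and all agreeing patients given the shared size. Then

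identical-group rate = (agreeing × 0.10 + circle implants × 0.30) / (agreeing + circle implants)

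| Sizes differ in | Identical group | Different group | Share of identical group matching both sizes |
|---|---|---|---|
| 20% (12) | (48 × 0.10 + 6 × 0.30)/54 = 12.2% | 30% | 48/54 = 89% |
| 40% (24) | (36 × 0.10 + 12 × 0.30)/48 = 15.0% | 30% | 36/48 = 75% |
| 60% (36) | (24 × 0.10 + 18 × 0.30)/42 = 18.6% | 30% | 24/42 = 57% |

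With the equal split, testing a match to the annular size gives the same figures. With 24 discordant patients split 18 annular and 6 circle, the circle contrast is (3.6 + 1.8)/42 = 12.9% versus 30%, and the annular contrast is (3.6 + 5.4)/54 = 16.7% versus 30%. Both methods still look favourable.

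**Dependence on the risk assumption.** With 20% risk in both strata the contrast is 20% versus 20%, and the spurious difference disappears.

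**With a true effect.** Take 24 discordant patients split 12 and 12, with true risks of 20% (circle size implanted) and 30% (annular size implanted), a difference of 10 points.
- Agreeing-patient risk 10%: (36 × 0.10 + 12 × 0.20)/48 = 12.5% versus 30%, or 17.5 points (exaggerated).
- Agreeing-patient risk 25%: (36 × 0.25 + 12 × 0.20)/48 = 23.75% versus 30%, or 6.25 points (diluted).

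**A second model, in which only an annular match matters.** Assume risk 20% if the implant matches the annular size and 40% if not. Of agreeing patients, 80% receive the shared size. Discordant patients split 45% annular, 45% circle and 10% neither. At 80% agreement:
- identical: (38.4 × 0.20 + 5.4 × 0.40)/43.8 = 22.5%
- different: (9.6 × 0.40 + 5.4 × 0.20 + 1.2 × 0.40)/16.2 = 33.3%

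The circle method appears better by 10.9 points, although among discordant patients the circle-size implants do worse by assumption (40% versus 20%).

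| Agreement | 100% | 90% | 80% | 70% | 50% | 30% |
|---|---|---|---|---|---|---|
| Apparent circle benefit (points) | 20.0 | 15.0 | 10.9 | 7.3 | 0.8 | −5.5 |

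The annular contrast is 20 points throughout.

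**Precision of the discordant subset.** For 12 versus 12 at 20% and 30%, SE = √(0.20 × 0.80/12 + 0.30 × 0.70/12) = 0.176. The approximate 95% interval is 10 ± 34 points, or −24 to +44. At assumed rates of 20% and 40%, two-sided alpha 0.05 and an equal split, power is about 7%, 11%, 15% and 22% with 6, 12, 18 and 30 discordant patients.

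**The case against.** Several points on the other side stand.

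- The zero-effect false contrast comes entirely from assuming higher risk where the sizes differ. That is confounding by anatomy, and stratifying or adjusting for that anatomy would address the same bias. A reader might infer a comparator fault wholly separate from covariate adjustment; the calculation does not show that.
- A reader might infer that the same data would validate annular sizing equally well. The two contrasts coincide only in special cases, such as full overlap or no effect with an equal split. In the second model the circle contrast nearly vanishes at 50% agreement and reverses at 30%. The documents do not say how often the conventional circle is chosen.
- Patients with equal sizes who received another size do inform the question as worded in Section 3.2.1, which is about concordant and discordant implants. Superiority over annular sizing is not a stated aim, and the Synopsis says there is no consensus technique.
- The appendix manual may already record the annular size.
- The project is an exploratory, retrospective pilot, and the discordant subset would be small and still subject to the operator's reasons for choosing a size.

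What remains is that nothing in the readable plan makes the separating comparison, while the stated purpose is validation. Recording a measurement would make that comparison possible but would not plan it.

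**Conclusion.** The point holds as a limit on attribution and should be fixed. The identical-versus-different comparison lacks a conventional-sizing reference, and an unknown share of the identical group may match both sizes. Those patients carry no information on what the circle method adds over annular sizing.

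If discordant patients are at higher risk, as the anatomy in Section 2.1 suggests, the comparison can favour the circle method with no true effect: 12.2% to 18.6% versus 30% across 20% to 60% disagreement, under the assumed 10% and 30% risks. A true effect can be exaggerated or diluted. Neither the size nor the direction can be fixed from the documents.

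A reader might go further and conclude that the project cannot answer its question at all, or that its primary contrast must be replaced. The documents do not support that: the comparison answers the concordance question as worded, and discordant patients are in the data but not singled out.

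**What to change.** - Have the CoreLab record the conventional (annular) size beside the circle-method size from the same 3mensio reading, unless the appendix manual already requires it.
- In Section 8.2, report complications by four categories of implanted size: matches both, circle only, annular only, neither. List separately the annuli above the sizing chart.
- Keep the stated comparison. Beside it, report implanted = circle size versus implanted = annular size among patients whose two sizes differ, as an estimate with a 95% confidence interval.
- State that an identical-versus-different result will not be attributed to the circle method over annular sizing unless this subset supports it.

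The cost is one extra CoreLab field, if it is not already collected, and a short addition to Section 8.2, with no new patients or scans. The drawback is a small subset with a wide interval, which may still be confounded by why the operator chose a given size. It is best settled before the CoreLab readings are linked to outcomes.

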3.3 TIMELINES

- Document preparation: Q1/early Q2 2022
- IRB/IEC approvals per site: from Q2/2022 ongoing
- Recruitment period: 6 months
- Follow-up: 30 days, 3 months

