3.4 PROJECT TERMINATION

The project ends after the last patient completes the observational period, all outstanding data queries are resolved, and all sites are closed. Participating sites will be notified in writing of the project completion.

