8 STATISTICAL ANALYSIS

8.1 SAMPLE SIZE DETERMINATION

Each site will recruit an average of 20 patients according to availability. A sample size of at least 60 patients in total is aimed for.

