8.2 DESCRIPTIVE ANALYSIS

Statistical analysis will be performed for the total study population. Continuous variables will be presented as mean \pm SD or as median with interquartile range, and categorical variables (e.g. gender) will be reported as frequencies and percentages. The Kolmogorov-Smirnov test will be used to test for normal distribution. For comparisons, Chi-Square or Fisher exact test will be used for categorical variables, and Student's t-test or Mann-Whitney U for continuous variables.

All statistical analyses will be performed using IBM SPSS Statistics version 29 (IBM, Armonk, New York) or R Core Team (<https://www.R-project.org/>).

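### The primary comparison of complications has no time window, the schedules merge 3 and 12 months into one entry, and no effect estimate with an interval is planned

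*Combined protocol and SAP*

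**What the plan says.** The primary objective (synopsis and section 3.2.1) asks whether patients "suffered from fewer complications if valve size was" identical to the circle-method size, compared with different from it. Neither place gives a time window, and section 3.2.3 lists the complications without one.

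Follow-up is described in four places:

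- Section 2.1, last paragraph: the method is to be validated by "evaluating the 30-day and 3-month outcomes of all consecutive patients".
- Section 3.3: "Follow-up: 30 days, 3 months".
- Synopsis, Schedule: "Baseline, Intervention, Discharge, 30 days, 3 months/12 months (according to availability, all retrospective".
- Section 7.4: complications are ticked at intervention, discharge, 30 days and a single column for 3/12 months. The death form uses that same last column.

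On analysis, section 8.2 reports categorical variables as counts and percentages and says that "Chi-Square or Fisher exact test will be used for categorical variables". No section names a risk difference, a ratio or a confidence interval. Section 8.1 says "A sample size of at least 60 patients in total is aimed for". The synopsis calls the work a pilot and states "No pre-specified statistical analyses, explorative approach".

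**The concern.** A complication proportion has a meaning only for a stated period at risk. If some patients contribute 3-month records and others 12-month records, according to what is available, the late proportion is neither a 3-month nor a 12-month risk and cannot be set against other series. The outcomes already exist in the records, so a time point left open can be settled after the results are known.

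The second gap is the estimate. In a small cohort, a non-significant Fisher test is easily read as showing no difference between patients whose valve matched the circle-method size and those whose valve did not. Only an estimate with its interval shows how little the data can exclude.

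**Working it through.** **Time points, side by side**

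| Place | 30 days | 3 months | 12 months |
|---|---|---|---|
| Section 2.1 | yes | yes | not mentioned |
| Section 3.3 | yes | yes | not mentioned |
| Synopsis, Schedule | yes, on its own | joined to 12 months | joined to 3 months |
| Section 7.4 | yes, on its own | joined to 12 months | joined to 3 months |
| Primary objective (synopsis, 3.2.1) | none | none | none |

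Section 2.1 comes nearest to fixing a time point, but it names two and ranks neither. The candidates are therefore two, or three if 12 months is in scope.

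**The plan's own figure.** 3 sites × a mean of 20 patients = 60, which matches section 8.1. It is a recruitment target. With no event rate, alpha, power or precision stated, nothing further can be reproduced.

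**Illustration.** These inputs are assumptions, not figures from the documents: an any-complication outcome with 30-day risk p0 of 10%, 20% or 30%, then a constant rate h of 0.5%, 1% or 2% per month.

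Step 1. Risk at month t: r(t) = 1 − (1 − p0) × exp(−h × (t − 1)).

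| p0 | h per month | r(3) | r(12) | Gap (points) |
|---|---|---|---|---|
| 10% | 0.5% | 10.90% | 14.82% | 3.92 |
| 10% | 2% | 13.53% | 27.77% | 14.24 |
| 20% | 0.5% | 20.80% | 24.28% | 3.49 |
| 20% | 2% | 23.14% | 35.80% | 12.66 |
| 30% | 0.5% | 30.70% | 33.75% | 3.05 |
| 30% | 2% | 32.74% | 43.82% | 11.08 |

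Results at 1% lie between these. A mixed late figure could fall anywhere in a gap of about 3.0 to 14.2 points.

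Step 2. Suppose the records were pooled, and 70% of one group but 30% of the other had 12-month records. With no true effect, the false difference is (0.7 − 0.3) × gap: from 0.4 × 3.05 = 1.2 points to 0.4 × 14.24 = 5.7 points.

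Step 3. Sampling error of the late risk difference, as a Wald 95% half-width: 1.96 × √[pA(1 − pA)/nA + pB(1 − pB)/nB]. The risks are those of step 2, with the imbalance taken in both directions.

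| Split of 60 | Half-width (points) |
|---|---|
| 30/30 | 16.9 to 24.6 |
| 40/20 | 17.8 to 26.2 |
| 45/15 | 19.3 to 28.5 |

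- Lowest: pA = 10.90 + 0.7 × 3.92 = 13.64%, pB = 10.90 + 0.3 × 3.92 = 12.07%, 30 per group. 1.96 × √(0.1364 × 0.8636/30 + 0.1207 × 0.8793/30) = 0.169.
- Highest: 36.07% in 45 patients, 40.50% in 15. 1.96 × √(0.3607 × 0.6393/45 + 0.4050 × 0.5950/15) = 0.285.

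Step 4. The same formula at 30 days, with equal risks in the two groups:

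- 10%, 30/30: 1.96 × √(0.09 × 2/30) = 15.2 points.
- 30%, 45/15: 1.96 × √(0.21 × (1/45 + 1/15)) = 26.8 points.

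Imprecision is of the same order at either time.

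**The case against.** The strongest reply is that the plan declares itself an exploratory pilot with no pre-specified analyses. It repeats this same comparison among its exploratory research questions, and section 3.2.3 lists the complications as exploratory endpoints. On that view an unranked time point follows from a declared choice. This stands in part: no confirmatory claim is made, and the missing time point alone would be missing detail. It does not settle whether 12 months is in scope, and a descriptive proportion needs a defined period too.

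Several stronger readings are tempting, and the documents do not support them:

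- **That 3- and 12-month records will be pooled, or that this biases the comparison.** The schedules permit pooling but do not announce it. Nothing shows that length of follow-up differs by size agreement. Even under the assumed 70%/30% imbalance, the false difference is well below the sampling error.
- **That every column in section 7.4 is a rival analysis, giving up to five.** Ticks at intervention and discharge show when complications are recorded. Section 2.1 points to 30-day and 3-month outcomes.
- **That only a p-value will be reported.** Section 8.2 also plans frequencies and percentages. If these are given by group, a reader could derive the difference; what is missing is a planned estimate with its interval.
- **That 30 days is the only time point common to all four places.** Three months is named in all four as well, though joined to 12 months in the two schedules.
- **That the end-of-project rule makes matters worse.** Section 3.4 says "The project ends after the last patient completes the observational period". The length of that period is unclear, but in a retrospective project this wording changes no patient's follow-up.

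A further limit stands: the illustrated risks presuppose a composite that the documents do not define. Naming a time point will not by itself say which complications are compared, or whether they are combined.

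**Conclusion.** The point holds in a limited form. Sections 2.1 and 3.3 disagree with the synopsis schedule and section 7.4 on whether 12 months belongs to follow-up. The primary comparison has no window, and no effect estimate with an interval is planned. The consequence is a late proportion that may have no clear meaning, and two or three time points that could each be offered as the answer.

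The half-width of roughly 17 to 29 points for a late difference (15 to 27 at 30 days) rests on assumed risks, group splits and an any-complication outcome, none of them in the documents. The gap of 3.0 to 14.2 points between the 3- and 12-month risks depends strongly on the assumed monthly rate. The harm is to interpretation rather than a demonstrated bias. The changes should be made because they cost almost nothing and improve on the stated plan.

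**What to change.** 1. Reconcile the synopsis schedule and sections 2.1, 3.3 and 7.4 on whether 12 months is in scope.
2. Split the 3/12-month entry into separate 3-month and 12-month records, and do not pool them.
3. Name one main time point for the primary comparison. Thirty days is a reasonable choice because it is the only post-discharge time point that stands alone in both schedules, and complications are already collected then.
4. At that time point, report the risk difference (identical versus different size) with a Newcombe or exact 95% confidence interval beside the planned tests, and the number in each group with no record at that time.
5. Report later time points separately, as secondary results.

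All of this can stay labelled exploratory. The cost is protocol wording, one more schedule column and one more statistic. If the eCRF, which is not among the documents, already records the two visits separately, no new data field is needed. No further patients or visits are required. The downside is that late events become secondary.
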